1.0 Introduction

The statistical analysis plan (SAP) describes the statistical methods to be used during the reporting and analyses of data collected under Bristol-Myers Squibb (BMS) Protocol MB130-068.

The Statistical Analysis Plan outlines the following:

- Study design
- Study objectives
- Endpoints
- Analysis populations
- Statistical methods
- Conventions and definitions

This SAP should be read in conjunction with the study protocol (Version 4.0, 30 January 2020) and electronic case report (eCRF) according to Page 1 of this document. Any further changes to the protocol or eCRF may necessitate updates to this SAP. Changes following approval of the first version SAP will be tracked in the SAP Change Log and a final version of the updated SAP will be approved prior to database lock.

2.0 Study Design

2.1 Overall Study Design

This is a multicenter, double-blind, placebo-controlled, randomized, parallel-group study to demonstrate the efficacy and safety of BMS-986036 in the treatment of participants with NASH (nonalcoholic steatohepatitis) and stage 3 liver fibrosis.

The study will consist of 4 periods:

- A Screening Period of up to 8 weeks in duration (this period may be extended to total of up to 12 weeks upon discussion with the medical monitor)
- A 48-week, Double-Blind Treatment Period, during which the participants will receive blinded study treatment (BMS-986036 10 mg, 20 mg, 40 mg once weekly (QW) or matching placebo QW)
- A 4-week Post-Treatment Follow-up [PTFU] Period
- A Follow-Up Period of up to 14 months (1 month is defined as 4 calendar weeks) after the Week 52/PTFU Visit for the collection of an additional dual-energy X-ray absorptiometry (DXA) assessment (in all participants), samples for potential immunogenicity testing (in all participants) as well as plasma and serum for biomarkers (in all participants) at 6 months (\pm 14 days) after the Week 52/PTFU visit. Subsequent visits at 9, 12, and 14 months after the Week 52 or PTFU visit will be performed in participants for whom Long-Term Immunogenicity Follow-Up Visits are required.

At the end of the Screening Period, participants meeting all inclusion and no exclusion criteria will enter the Double-Blind Treatment Period.

Participants will be enrolled and randomized via interactive response technology (IRT) to receive BMS-986036 10 mg QW, BMS-986036 20 mg QW, BMS-986036 40 mg QW or matching placebo QW in a 1:1:1:1 ratio. A liver biopsy will be performed during the Screening Period (if historical biopsy meeting protocol requirements is not available) and at Week 24 in all participants. A total of approximately 160 participants was planned to be randomized (40 participants per arm). The final number of participants randomized was 197 participants.

The study arms were as follows.

Arm 1: BMS-986036 (10 mg QW)

Arm 2: BMS-986036 (20 mg QW)

Sponsor: Bristol-Myers Squibb

Protocol no: MB130-068

Arm 3: BMS-986036 (40 mg QW)

Arm 4: Placebo

Participants will be stratified at randomization by country (Non-Japan versus Japan). Participants in Non-Japan (countries other than Japan) will be stratified at randomization according to Type 2 Diabetes Mellitus (T2DM) status (yes versus no) and nonalcoholic fatty liver disease (NAFLD) Activity Score (NAS) (≤ 5 versus > 5). Japanese participants will not be further stratified.

[figure not shown]
The number of participants with NAS of < 4 will not exceed 15% of the total number of randomized participants.

Randomized participants will receive their assigned double-blind study treatment for a total of 48 weekly doses. The treatment will be administered by subcutaneous (SC) injection of 2 prefilled syringes of study treatment in the abdomen according to their assigned treatment arm. During the Double-Blind Treatment Period, participants will be evaluated for safety and efficacy every 4 weeks (± 5 days) through Week 24 and every 8 weeks (± 5 days) after Week 24 through Week 48.

Participants will then return at Week 52 (± 5 days) for a PTFU Visit. Participants who discontinue study treatment earlier than Week 48 will have an Early Termination (ET) Visit at the time of study treatment discontinuation and will return for a PTFU Visit 4 weeks (± 5 days) after the ET Visit.

Participants will return 6 months (± 14 days) (1 month is defined as 4 calendar weeks) after the Week 52/PTFU Visit for DXA to assess BMD and for collection of samples for potential immunogenicity testing as well as serum and plasma biomarker samples. Participants may need to return at 9 months, 12 months, and 14 months (± 14 days) after the Week 52/PTFU Visit if required for immunogenicity testing.

[figure not shown]
A schematic of the study design is displayed in [Figure 1](#) (Screening to Week 52/Post-Treatment Follow-up [PTFU]) and [Figure 2](#) (BMD and immunogenicity follow-up visits after the Week 52/PTFU Visit).

Sponsor: Bristol-Myers Squibb

Protocol no: MB130-068

[figure not shown]
Figure 1. Study Design Schematic – Screening to Week 52/PTFU

ET = early termination; PTFU = Post-Treatment Follow-Up; QW = once weekly

* For participants who discontinue study medication prematurely, liver biopsy will be performed at ET if the participant has completed at least Week 20 and has not had a Week 24 biopsy. If a participant discontinues study participation prior to Week 20 they should consider having a liver biopsy at ET.

Figure 2. Study Schematic – Bone Mineral Density and Immunogenicity Follow-Up Visits After the Week 52/PTFU Visit (visit windows ± 14 days) (1 month is defined as 4 calendar weeks)

DXA = dual-energy X-ray absorptiometry ET = early termination; PTFU = Post-Treatment Follow-Up; QW = once weekly

* All participants will return 6 months (± 14 days) (1 month is defined as 4 calendar weeks) after the Week 52/PTFU Visit for dual-energy X-ray absorptiometry (DXA) to assess bone mineral density (BMD) and for collection of samples for potential immunogenicity testing as well as serum and plasma biomarker samples. Participants will return at 9 months, 12 months, and 14 months (visit windows ± 14 days) (1 month is defined as 4 calendar weeks) after the Week 52/PTFU Visit if required for immunogenicity testing (See Section 8.5.3.6).

Sponsor: Bristol-Myers Squibb

Protocol no: MB130-068

2.2 Sample Size Considerations

The primary efficacy endpoint is the proportion of participants who achieve a ≥ 1 -stage improvement (as defined by NASH Clinical Research Network (CRN) Fibrosis Score) in fibrosis without worsening of NASH or NASH improvement (as defined by NAS) with no worsening of fibrosis at Week 24, as determined by liver biopsy.

It was planned to randomize approximately 160 participants to 1 of the 4 treatment groups (approximately 40 participants per group), BMS-986036 10 mg QW, BMS-986036 20 mg QW, BMS-986036 40 mg QW or matching placebo QW in a 1:1:1:1 ratio.

A Cochran-Armitage trend test of proportions, with an estimated response rate of 15% for the primary endpoint for placebo and response rates for BMS-986036 10 mg QW, BMS-986036 20 mg QW, and BMS-986036 40 mg QW of 20%, 30%, and 40%, respectively, would provide at least 80% power at a 1-sided $\alpha = 0.05$. (based on the original sample size estimate of 160 participants). The final sample size was 197 participants.

2.3 Randomization

Randomization will be conducted in the following manner:

- Eligible participants will be randomized by the IRT using a pre-specified schedule in a double-blind manner to 10 mg BMS-986036, 20 mg BMS-986036, 40 mg BMS-986036, or placebo arms in a 1:1:1:1 ratio based on the stratification factors specified in protocol Section 9.3 (or Section 2.4 of the SAP).
- The IRT will provide study treatment kit numbers that contain the appropriate study treatment (BMS-986036 or placebo) for dispensation to that participant.

At subsequent study visits, the investigator or designee will access the IRT to receive the corresponding kit numbers assigned to the participant for the purpose of dispensing study treatment.

2.4 Stratification Factors

Randomization of participants will be stratified by country (non-Japan versus Japan). Participants in countries other than Japan will be stratified at randomization according to T2DM status (yes versus no) and NAS (≤ 5 versus > 5). Japanese participants will not be further stratified.

2.5 Unblinding Information

The Data Monitoring Committee (DMC) provides oversight of safety considerations throughout the study. A separate unblinded team, comprised of an unblinded Independent Reporting Statistician (IRS) and unblinded programmer(s), will produce output for the DMC using masked treatments. Treatment decodes may only be requested by the DMC Chair and will be provided by the IRS. Data summaries and listings will be transmitted via a secure portal by the IRS to only the DMC members. Additional details regarding the DMC process and unblinding are provided in the DMC charter.

Study data for all participants through Week 24 will be analyzed by pre-specified unblinded individuals when all participants have completed the assessments required for the Week 24 (or ET) visit. Refer to SAP Section 7.2 for additional details.

Sponsor and designee personnel may be unblinded once all participants have completed the Week 52/PTFU Visit and all data have been collected through that time point to facilitate analyses. Designated sponsor staff may be unblinded (obtain the randomization codes) prior to database lock to facilitate the bioanalytical analysis of PK samples and immunogenicity. A bioanalytical scientist in the sponsor Bioanalytical Sciences department (or a designee in the external central bioanalytical laboratory) will be unblinded to (may obtain) the randomized treatment assignments in order to minimize unnecessary bioanalytical analysis of samples.

Sponsor: Bristol-Myers Squibb

Protocol no: MB130-068

2.6 Clarification from Protocol

- Study medication is defined as any investigational treatment(s), marketed product(s), placebo or medical device intended to be administered to a study participant according to the study randomization or treatment allocation.
- For the purposes of the calculations contained in this SAP, study treatment will include only doses of BMS-986036 or placebo.

3.0 Study Objectives

3.1 Primary Efficacy Objective

The primary efficacy objective of this study is as below.

- To evaluate the efficacy of BMS-986036 in adults with NASH and stage 3 liver fibrosis based on:
 - 1) Improvement of fibrosis without worsening of NASH, OR
 - 2) NASH improvement with no worsening of fibrosis, as determined by liver biopsy at Week 24.

Improvement in fibrosis is defined as a decrease of fibrosis by ≥ 1 point, as determined by the NASH CRN Fibrosis Score. Worsening of fibrosis is defined as an increase of fibrosis by ≥ 1 point, as determined by the NASH CRN Fibrosis Score. Worsening of NASH is defined as an increase of the NAFLD Activity Score (NAS) by ≥ 1 point. NASH improvement is defined as a decrease of NAS by ≥ 2 points (with contribution from > 1 NAS component).

3.2 Secondary Efficacy Objectives

The secondary efficacy objectives of this study are:

- To evaluate the impact of BMS-986036 on improvement of fibrosis as determined by liver biopsy at Week 24
- To evaluate the impact of BMS-986036 on collagen proportionate area (CPA) on liver biopsy at Week 24
- To evaluate the impact of BMS-986036 on resolution of NASH without worsening of fibrosis, as determined by liver biopsy at Week 24
- To evaluate the impact of BMS-986036 on resolution of NASH, as determined by liver biopsy at Week 24
- To evaluate the impact of BMS-986036 on improvement of fibrosis without worsening of NASH
- To evaluate the impact of BMS-986036 on improvement of NASH without worsening of fibrosis, as determined by liver biopsy at Week 24
- To evaluate the impact of BMS-986036 on improvement of NASH, as determined by liver biopsy at Week 24
- To evaluate the effect of BMS-986036 on progression to cirrhosis, as determined by liver biopsy at Week 24

3.3 Safety Objectives

The safety objectives of this study are to demonstrate the safety of BMS-986036 in adults with NASH and stage 3 liver fibrosis throughout the course of the study, including bone mineral density and immunogenicity.

Sponsor: Bristol-Myers Squibb

Protocol no: MB130-068

3.4 Pharmacokinetic Objectives

- To determine trough concentrations of BMS-986036 in all participants

3.5 Exploratory Objectives

To explore the impact of BMS-986036 administration on the following parameters:

- Quantitative assessments of fibrosis and fat on biopsy
- NAS
- Digital pathology assessment of fibrosis and NASH
- Hepatic fat fraction by magnetic resonance imaging-proton density fat fraction (MRI-PDFF)
- Noninvasive measures of fibrosis and/or cirrhosis
- Metabolic assessments
- Patient-reported outcomes
- Exploratory biomarkers

4.0 Endpoints

4.1 Primary Efficacy Endpoint

The primary efficacy endpoint of this study is the proportion of participants who achieve a ≥ 1 -stage improvement (as defined by NASH CRN Fibrosis Score) in fibrosis without worsening of NASH or NASH improvement (as defined by NAS) with no worsening of fibrosis (as defined by NASH CRN Fibrosis Score) at Week 24 as determined by liver biopsy.

For this protocol, improvement in fibrosis is defined as a decrease of fibrosis by ≥ 1 point, as determined by the NASH CRN Fibrosis Score. Worsening of fibrosis is defined as an increase of fibrosis by ≥ 1 point, as determined by the NASH CRN Fibrosis Score. Worsening of NASH is defined as an increase of the NAFLD Activity Score (NAS) by ≥ 1 point. NASH improvement is defined as a decrease of NAS by ≥ 2 points (with contribution from > 1 NAS component).

4.2 Secondary Efficacy Endpoints

The secondary efficacy endpoints are the proportion of participants with the following:

- NASH CRN Fibrosis Score $>=1$ stage improvement at Week 24
- Ishak Score $>=1$ stage improvement at Week 24
- Any CPA decrease at Week 24
- NASH resolution (NAS component of ballooning = 0 and inflammation = 0-1) without worsening of fibrosis (as defined by NASH CRN Fibrosis Score) at Week 24
- NASH resolution (NAS component of ballooning = 0 and inflammation = 0-1) at Week 24
- NASH improvement (reduction of NAS by ≥ 2 points with contribution from > 1 NAS component) without worsening of fibrosis at Week 24
- Achieve a ≥ 1 -stage improvement (as defined by NASH CRN Fibrosis Score) in fibrosis without worsening of NASH
- NASH improvement (reduction of NAS by ≥ 2 points with contribution from > 1 NAS component) at Week 24
- Progression to cirrhosis (as defined by NASH CRN Fibrosis Score) at Week 24

Sponsor: Bristol-Myers Squibb

Protocol no: MB130-068

4.3 Safety Endpoints

Safety will be assessed by evaluating endpoints as discussed in this section.

4.3.1 Adverse Events

- Incidence and frequency of treatment-emergent adverse events (AEs) and serious adverse events (SAEs).

The definition of AEs and SAEs as well as their time periods for collection can be found in the Protocol Section 8.5.3.1 and Protocol Appendix 8.

Adverse events of special interest (AESI) will include following AEs:

1. Injection site reactions (injection-site erythema and edema)
2. Gastrointestinal events (Diarrhea, frequent bowel movements, nausea, vomiting, abdominal pain)
3. Bone-related events (Osteoporosis, osteopenia, bone and joint injuries, fractures (except tooth fracture), endocrine abnormalities of gonadal function not elsewhere classified (NEC), hyperparathyroid disorders, hypoparathyroid disorders, parathyroid disorders NEC, parathyroid analyses, metabolic bone disorders, vitamin D abnormal, vitamin D decreased, vitamin D deficiency, and miscellaneous events related to bone density)

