6.3.2.3 Injection Reactions

Injection site reactions have been monitored in completed and ongoing studies using the Draize scale, which rates erythema and edema at the injection site on a scale ranging from “none” to “severe.” In Phase 1 and Phase 2a studies, injection-related AEs were generally mild, transient, resolved without intervention, and did not lead to discontinuation.

In the single ascending dose portion of Study MB130001, 2 participants (5.6%) who received BMS-986036 and 0 participants in the placebo group developed injection site erythema. In the multiple ascending dose portion of the study, the proportion of participants who developed erythema was well balanced between treatment groups (BMS-986036 at any dose versus placebo). Eleven participants developed injection site erythema (8 participants [22.2%] across all BMS-986036 groups and 3 participants [25.0%] in the placebo group). No participants developed injection site edema.

In Study MB130002, injection site erythema and/or injection site edema were reported in 4 of 96 participants (4.2%) who received BMS-986036 and in 1 of 24 participants (4.2%) who received placebo. One injection site reaction (20 mg QD) was of severe intensity, and the remaining 3 injection site reactions were rated as mild in intensity. Concurrent ADAs were present in 1 participant (10 mg QD) of the 5 participants with injection site erythema and/or edema.

In Study MB130045, injection site erythema was reported in 3 (4.0%) participants, and injection site edema was reported in 1 (1.3%) participant. All AEs of injection site erythema and injection site edema were mild or moderate in intensity. Concurrent ADAs were present in 2 participants (20 mg QW and 10 mg QD) of the 3 participants with injection site erythema and/or edema.

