The method of evaluating intensity and assessing causality of AEs and SAEs and the procedures for completing and reporting/transmitting SAE reports are provided in [Appendix 8](#).

Method of Detecting AEs and SAEs

AEs can be spontaneously reported or elicited during open-ended questioning, examination, or evaluation of a participant. Care should be taken not to introduce bias when collecting AE and/or SAEs. Inquiry about specific AEs should be guided by clinical judgment in the context of known AEs, when appropriate for the program or protocol.

Follow-Up and Recording of AEs and SAEs

- Nonserious AEs should be followed to resolution or stabilization, or reported as SAEs if they become serious (see [Appendix 8](#))

- Follow-up is also required for nonserious AEs that cause interruption or discontinuation of study medication and for those present at the end of study medication, as appropriate
- All nonserious AEs and SAEs must be recorded and described on the corresponding pages of the eCRF. Completion of supplemental eCRFs may be requested for AEs/SAEs and/or laboratory abnormalities that are reported/identified during the course of the study

After the initial AE/SAE report, the investigator is required to proactively follow each participant at subsequent visits/contacts. All SAEs and nonserious AEs of special interest (as defined in [Section 8.5.3.7](#)) will be followed until resolution, until the condition stabilizes, until the event is otherwise explained, or until the participant is lost to follow-up (as defined in [Section 8.3.9.3](#)).

Further information on follow-up procedures is given in [Appendix 8](#).

Regulatory Reporting Requirements for SAEs

- Prompt notification by the investigator to the sponsor of SAEs is essential so that legal obligations and ethical responsibilities towards the safety of participants and the safety of a product under clinical investigation are met
- An investigator who receives an investigator safety report describing SAEs or other specific safety information (e.g., summary or listing of SAEs) from the sponsor will file it along with the IB and will notify the IRB/IEC, if appropriate according to local requirements

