9.5.3 Safety Analyses

Safety analyses will be performed using the As Treated population. For analysis, all treatment-emergent (i.e., occurring after the first dose of study medication) AEs, SAEs, and AEs of special interest will be summarized by system organ class, preferred term, and treatment. Vital signs, immunogenicity, BMD, and laboratory data will be summarized by treatment. ECG abnormalities, physical examination abnormalities, if present, will be summarized.

Responses of anti-BMS-986036 antibodies and anti-FGF21 antibodies will be listed and tabulated by treatment and study day. The relationship between immunogenicity and PK and/or PD may be explored.

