6.2 Safety Analyses

6.2.1 Adverse Events

All adverse events will be presented based on the safety population by treatment group, and pooled BMS-986036.

A summary of treatment-emergent AEs, including the number of events reported and the number and percentage of participants reporting

- at least one AE
- any severe AE
- any treatment-related AE
- any AEs of special interest
- any severe treatment-related AE
- any AE with outcome of death

Sponsor: Bristol-Myers Squibb

Protocol no: MB130-068

- any serious AE
- any treatment-related SAE
- any AE leading to the discontinuation of study treatment
- any treatment-related AE leading to the discontinuation of study treatment
- any AE leading to discontinuation of the study
- any treatment-related AE leading to discontinuation of the study

A breakdown of the number and percentage of participants reporting each AE, categorized by system organ class (SOC) and preferred term (PT) will be presented. Maximum severity will be summarized for all TEAE by SOC and PT. Counts for AEs will be by participant not event and participants are only counted once within each SOC or PT.

Only treatment-emergent AEs will be summarized in tables. All AEs will be included in listings. In addition DILI will be presented graphically.

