8.5 Adverse Events of Special Interest

The sponsor has developed a list of AEs of Special Interest for the BMS-986036 program based on the known biologic class effects, the mechanism of action, and clinical study data. These will include the following:

- Injection site reactions
- Gastrointestinal events (Diarrhea, frequent bowel movements, nausea, vomiting, abdominal pain)
- Bone-related events (Osteoporosis, osteopenia, bone and joint injuries, fractures (except tooth fracture), endocrine abnormalities of gonadal function not elsewhere classified (NEC), hyperparathyroid disorders, hypoparathyroid disorders, parathyroid disorders NEC, parathyroid analyses, metabolic bone disorders, vitamin D abnormal, vitamin D decreased, vitamin D deficiency, and miscellaneous events related to bone density)

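### SAP 4.3.1 restricts injection-site AESIs to erythema and edema, SAP 8.5 and Protocol 8.5.3.7 do not, and SAP 6.2.1 does not say which set its AESI row counts

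*SAP*

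**What the plan says.** AESIs are defined in three itemised lists.

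- SAP 4.3.1, in the safety endpoints section, gives as its first item "Injection site reactions (injection-site erythema and edema". Gastrointestinal and bone-related events follow, each with its qualifying terms in parentheses.
- SAP 8.5, under conventions and general definitions, repeats the gastrointestinal and bone lists with the same parenthetical terms. Its first item is only "Injection site reactions".
- Protocol 8.5.3.7 has the same unqualified entry, again beside itemised gastrointestinal and bone terms. Protocol 6.3.3 also names injection site reactions without restriction.

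Three places use the definition.

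- SAP 6.2.1 reports, by treatment group and for pooled drug, the number and percentage of participants with "any AEs of special interest". It does not say which section supplies the set.
- Protocol 9.5.3 promises that "AEs, SAEs, and AEs of special interest will be summarized by system organ class, preferred term, and treatment".
- Protocol 8.5.3.1 sets the follow-up rule. "All SAEs and nonserious AEs of special interest", with a pointer to Section 8.5.3.7, are followed until they resolve, stabilise or are explained, or the participant is lost.

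**The concern.** A programmer working from SAP 4.3.1 and one working from SAP 8.5 could fill the same table row with different counts from the same data. Under 4.3.1, the row would also leave out some events that the protocol classes as AESIs and that sites have followed as AESIs.

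Injection reactions are one of the risks the protocol names for this drug. Each participant is due 2 injections a week for 48 weeks, or 2 × 48 = 96 injections. The AESI summary is where a reader would look for such reactions, so it should cover what the protocol says it covers.

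**Working it through.** The plan states no figure for this point, so the check is a comparison of the texts followed by the little arithmetic they allow.

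**1. Do the lists differ?** The gastrointestinal and bone terms agree between SAP 4.3.1 and SAP 8.5. Injection-site reactions are the only category that differs: two named terms in 4.3.1, no terms in 8.5.

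**2. Is the parenthesis in 4.3.1 a restriction or an illustration?** It has no wording that marks it as an example. The two parentheses beside it work as definitions, and the bone list even carries an exclusion, for tooth fracture. Reading the first one the same way is the natural reading.

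**3. Does anything give one section precedence?** No. SAP 4.3 says safety is assessed through the endpoints in that section, which supports 4.3.1. SAP 8.5 sits among the general definitions, which supports 8.5. SAP 6.2.1 refers to neither.

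**4. What happens to one participant?** Take someone whose only AESI-type event is injection-site pruritus.

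- Protocol 8.5.3.7: an AESI, so followed under 8.5.3.1.
- SAP 8.5: counted in the 6.2.1 row.
- SAP 4.3.1: not counted in that row.
- General table by system organ class and preferred term in SAP 6.2.1: listed either way.

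**5. How far does one such participant move the row?** Inputs: 197 randomised, about 49 per arm (Protocol 6.2). The safety population is taken to be close to this.

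- One arm: 1/49 = 2.0 percentage points.
- Pooled drug: 197 − 49 = 148, and 1/148 = 0.7 points.

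A participant who also has a gastrointestinal, bone or erythema/edema AESI is already in the row and moves it by nothing.

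**6. Can the total be sized?** No. It needs the proportion of participants whose only AESI is an injection-site reaction other than erythema or edema, and the documents give no such rate. The figures in Protocol 6.3.2.3 are for events that both definitions include. In Study MB130002, "injection site erythema and/or injection site edema were reported in 4 of 96 participants (4.2%) who received BMS-986036". In the multiple-dose part of MB130001, erythema occurred in "8 participants [22.2%] across all BMS-986036 groups". These describe the narrow category, not the gap between the two definitions.

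**7. Can a count comparable with those earlier figures be read from the preferred-term rows?** No. The MB130002 figure counts participants with erythema, edema or both. SAP 6.2.1 counts each participant once within each preferred term, so someone with both appears in two rows. Protocol 6.3.2.3 shows this for MB130045: 3 participants with erythema and 1 with edema, which add to 4, yet it refers to 3 participants with either or both.

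**The case against.** The strongest reply is that the two SAP sections can be reconciled. SAP 8.5 closely follows the protocol list and is silent on terms; SAP 4.3.1 supplies them. The protocol's background section offers a source for the wording: "Injection site reactions have been monitored in completed and ongoing studies using the Draize scale, which rates erythema and edema at the injection site". On this view the parenthesis clarifies the category. That is a plausible origin, but the text is background on other studies and does not define AESIs for this one. It also leaves the SAP narrower than Protocol 8.5.3.7.

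A second reply is that the SAP text is not the programming specification. Both documents say the sponsor has developed an AESI list for the program, and the table shells are kept outside the SAP. The bone category ends in a miscellaneous entry that could not be programmed without a term list. This stands: shells or a coding list may already settle the choice, so different counts are possible but not shown.

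A third reply is that little depends on it. Follow-up is tied to Protocol 8.5.3.7 and does not change. No test or efficacy result is involved. This also stands.

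A reader might go further and infer that the narrow list would shift AESI percentages by many points or distort the drug-placebo contrast. The documents do not support that. Any such figure needs an assumed rate of other injection-site reactions and an assumed overlap with other AESIs. The available gastrointestinal rates (72% on drug, 28% on placebo, Protocol 6.3.2.1) cover all gastrointestinal events, including some that are not AESIs. The earlier injection-site figures also show no excess on drug: erythema 22.2% against 25.0% on placebo in MB130001, and erythema and/or edema 4.2% in both groups in MB130002.

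**Conclusion.** The contradiction is real. SAP 4.3.1 states an endpoint rule narrower than the AESI definition in SAP 8.5 and Protocol 8.5.3.7, and SAP 6.2.1 does not choose between them. Followed as written, 4.3.1 drops some protocol-defined AESIs from the AESI count.

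The consequence is small and descriptive. Each participant whose only AESI is another kind of injection-site reaction moves the row by about 2.0 points in an arm of 49, or 0.7 points for pooled drug. How many such participants there will be is unknown, and if there are none the two counts agree. It would be wrong to conclude that these events vanish from the report, because each remains in the general adverse event table. The conclusion assumes that no document outside the protocol and SAP already fixes the term set.

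**What to change.** In SAP 4.3.1, delete the parenthesis after injection site reactions, or replace the list with a reference to SAP 8.5, so that one definition matches Protocol 8.5.3.7. Define the category as all injection-site reaction preferred terms, ideally through a MedDRA term list, because deleting the parenthesis alone still leaves the choice of terms open. State that this set defines the AESI row in SAP 6.2.1 and the AESI summary promised in Protocol 9.5.3.

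If comparison with the earlier studies is wanted, add a separate row counting participants with erythema and/or edema.

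The cost is one deletion, one cross-reference and a term list, with no new data collection. SAP 1.0 already provides for logged changes before database lock. The downside is that the broader count is not directly comparable with the earlier erythema and edema rates, which is what the optional row is for.
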